9.7.3. Analysis of exploratory objectives

Patient demographic, clinical characteristics and treatment outcomes will be reported for Cohort 1 and Cohort 2 (See Section 9.3.1.3 for variable definitions). If multiple records for a variable exist during the baseline period, the record closest to index will be chosen. The number of missing values will be reported for each variable, and percentages for categorical variables will be based on non-missing values. Time from diagnosis to 1L treatment, time to next treatment and duration of treatment by LOT will be estimated using KM methods to obtain median estimates with 95% CIs and IQRs.

HCRU including number of visits and days of hospitalization will be summarized as counts (n) and proportions (%). Direct medical cost will be summarized using mean, median and IQR.

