9.2.2. Study population

Inclusion criteria:

- Patient has two or more documented clinical visits in the National Anti-Tumor Drug Surveillance System (NATDSS) network on or after January 1, 2013.
- Patient has a confirmed diagnosis of DDLPS during his/her lifetime.
- At least 18 years old at the date of initial diagnosis

No exclusion criteria are applied.

Eligible population will be divided into two groups:

NIS Protocol BI Study Number 1403-0024

Page 13 of 37 C42272174

Proprietary confidential information© 2023 Boehringer Ingelheim GmbH or one or more of its affiliated companies

- Cohort 1 will include unresectable locally advanced or metastatic DDLPS patients who received at least one line of systemic antineoplastic treatment by the end of cohort identification period (index date = start date of 1L treatment).
- Cohort 2 will include patients with DDLPS who have not initiated 1L systemic antineoplastic treatment by the end of cohort identification period (index date = date of initial DDLPS diagnosis during cohort identification period). Patients initiated 1L treatment afterwards or patients received adjuvant and/or neoadjuvant therapy only through follow-up will be included in Cohort 2.

In both cohorts, 1L therapy will be defined as the initial set of drugs used after unresectable locally advanced or metastatic diagnosis. Metastatic patients will be defined as those with metastatic diagnosis or presence of metastatic sites; unresectable locally advanced patients will be defined as those with advanced diagnosis and without subsequent surgical resection.

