6.3 STUDY POPULATION

Inclusion criteria:

- Patient has two or more documented clinical visits in the National Anti-Tumor Drug Surveillance System (NATDSS) network on or after January 1, 2013.
- Patient has a confirmed diagnosis of DDLPS during his/her lifetime.
- At least 18 years old at the date of initial diagnosis

No exclusion criteria are applied.

Eligible population will be divided into two groups:

- Cohort 1 will include unresectable locally advanced or metastatic DDLPS patients who received at least one line of systemic antineoplastic treatment by the end of cohort identification period (index date = start date of first line (1L) treatment).
- Cohort 2 will include patients with DDLPS who have not initiated 1L systemic antineoplastic treatment by the end of cohort identification period (index date = date of initial DDLPS diagnosis during cohort identification period). Patients initiated 1L treatment afterwards or patients received adjuvant and/or neoadjuvant therapy only through follow-up will be included in Cohort 2.

In both cohorts, 1L therapy will be defined as the initial set of drugs used after unresectable locally advanced or metastatic diagnosis. Metastatic patients will be defined as those with metastatic diagnosis or presence of metastatic sites; unresectable locally advanced patients will be defined as those with advanced diagnosis and without subsequent surgical resection.

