Missing / Unknown		
Total lines of treatment (categorized), N (%)		
1		
2		
3		
4		
≥5		
Missing / Unknown		

Abbreviations: N = number; SD = standard deviation; IQR = interquartile range; min = minimum; max = maximum.

Statistical and Epidemiological Analysis Plan (SEAP) for Observational and Non-Interventional Studies (ONIS) Page 28 of 36

Table 6. Treatment types for Cohort 1 and Cohort 2 by line of therapy

V 1	Cohort 1,				Cohort 2,		
	N=				N =		
	1L	2L	3L	_	1L	2L	3L

Treated, N (%)

Yes

No

Regimens, N (%)

Doxorubicin

Epirubicin

Liposomal doxorubicin

AD (doxorubicin, dacarbazine)

AIM (doxorubicin, ifosfamide, mesna)

Ifosfamide, epirubicin, mesna

Larotrectinib (NTRK fusion pos sarcomas only)

Entrectinib (NTRK fusion pos sarcomas only)

Pazopanib

Eribulin

Trabectedin

AD LMS only (doxorubicin, dacarbazine)

Gemcitabine and docetaxel

Gemcitabine

Gemcitabine and vinorelbine

Gemcitabine and dacarbazine

Dacarbazine

Ifosfamide

Temozolomide

Vinorelbine

Regorafenib

MAID (mesna, doxorubicin, ifosfamide, dacarbazine)

Statistical and Epidemiological Analysis Plan (SEAP) for Observational and Non-Interventional Studies (ONIS)

Page 29 of 36

	Cohort 1,			Cohort 2,			
		N =			N=		
·	1L 2L 3L		1L	2L	3L		

Pembrolizumab

durvalumab

Other

Concurrent steroid therapy, N (%)

Yes

No

Concurrent immunosuppressant therapy, N (%)

Yes

No

Concurrent hormone replacement therapy, N (%)

Yes

No

Abbreviations: 1L = first line; 2L = second line; 3L = third line.

Notes: Specific treatments and categories are ordered from highest to lowest frequency and may change upon examination of the data.

Statistical and Epidemiological Analysis Plan (SEAP) for Observational and Non-Interventional Studies (ONIS)

Page 30 of 36

Table 7. Time to next treatment	by l	line of	f treatment f	for	Cohort 1	and	Cohort 2
---------------------------------	------	---------	---------------	-----	----------	-----	----------

	Cohort 1,	Cohort 2,
	N =	N=
Treated, N (%)		
Yes		
No		
Time from diagnosis to 1L treatment, months Median, [95% CI]		
IQR		
Fime from 1L treatment to 2L treatment, months Median, [95% CI]		
IQR		
Time from 2L treatment to 3L treatment, months Median, [95% CI]		
IQR		

Abbreviations: CI = confidence interval; IQR = interquartile range; 1L = first line; 2L = second line; 3L = third

Statistical and Epidemiological Analysis Plan (SEAP) for Observational and Non-Interventional Studies (ONIS)

Page 31 of 36

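### Time from diagnosis to 1L is to be estimated by Kaplan-Meier within cohorts defined by whether 1L had started by 31 December 2021: the Cohort 2 median is wrong by construction, and the Cohort 1 median describes only patients treated by then.

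*Protocol*

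**What the plan says.** Protocol 9.7.3 plans medians, 95% CIs and IQRs: "Time from diagnosis to 1L treatment, time to next treatment and duration of treatment by LOT will be estimated using KM methods". That sentence does not itself say that the cohorts are analysed apart. The split comes from the start of the same section, where "treatment outcomes will be reported for Cohort 1 and Cohort 2", and from SAP Annex 2, Table 7. The row there headed "Time from diagnosis to 1L treatment, months" has a Cohort 1 column and a Cohort 2 column, and no combined column.

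Protocol 9.2.2 and SAP 6.3 define the cohorts by 1L status at the end of the identification period, which Protocol 9.2.3 and SAP 6.4 set at 31 December 2021:

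- Cohort 1: patients with unresectable locally advanced or metastatic disease who "received at least one line of systemic antineoplastic treatment by the end of cohort identification period".
- Cohort 2: "patients with DDLPS who have not initiated 1L systemic antineoplastic treatment by the end of cohort identification period". Late starters stay there: "Patients initiated 1L treatment afterwards or patients received adjuvant and/or neoadjuvant therapy only through follow-up will be included in Cohort 2".

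Follow-up ends on 31 December 2022. Censoring for survival and treatment patterns is at last activity. The visible text has no combined analysis of time to 1L and no competing-risk rule for death before 1L. Table 2 of SAP Annex 2 has a row for initial diagnoses before 2013.

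**The concern.** Starting 1L is both the event of this variable and the rule that assigns patients to columns. Kaplan-Meier assumes that a patient still under observation at a given wait could have the event then. Neither column meets this.

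In Cohort 2, all time from diagnosis to the cut-off is event-free because of how the cohort was chosen. In Cohort 1, every member has the event, so nothing is censored and the curve is simply the distribution of waits among those treated in time.

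Set side by side, the two medians would look like a short wait in one group and a very long wait in another, when the contrast is produced by the sorting rule. What a reader would want from this row is how many DDLPS patients reach 1L and how fast. Neither column gives that.

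**Working it through.** The documents give no figure for time to 1L, so there is none to reproduce. The check is a reading of the membership rules, followed by illustrations.

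**Inputs from the documents.** Cohort split at 31 December 2021, which is 108 months after 1 January 2013; end of follow-up at 120 months.

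**Assumptions, not from the documents.** Exponential waits T with rate λ = ln 2 / (true median). Diagnosis date X uniform over 0 to 108 months unless stated. No death or loss unless stated.

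**Step 1, Cohort 2.** Membership requires X + T > 108 or no 1L at all. A patient diagnosed on 1 January 2018 has 48 months to the cut-off in which an event is impossible; only waits of 48 to 60 months can count. Simulated Kaplan-Meier medians in months:

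| True median | Cohort 2, no death or loss | Cohort 2, range over death (none, or median 36 months) and loss (0 or 1% a month) |
|---|---|---|
| 6 | 14.7 | 14.7-23.5 |
| 12 | 34.2 | 34.2-52.3 |
| 24 | 83.9 | 83.9-93.8 |
| 60 | not reached | not reached |

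If 30% to 70% of patients never need 1L (true median 12 in the rest, no death or loss), the Cohort 2 median is also not reached.

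**Step 2, Cohort 1 with no diagnosis before 2013.** A wait of w months fits only if X ≤ 108 − w, so the density of waits is proportional to λ·exp(−λw)·(108 − w), and long waits are under-represented. True medians of 12, 18 and 24 give 10.0, 13.5 and 16.1. The shortfalls are (12 − 10.0)/12 = 17%, (18 − 13.5)/18 = 25% and (24 − 16.1)/24 = 33%.

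**Step 3, Cohort 1 with earlier diagnoses.** Cohort 1 is indexed on 1L start, and Table 2 allows initial diagnoses before 2013. If diagnoses reach back H months at a steady rate, any wait w ≤ H can begin anywhere in a stretch of 108 months, so its weight no longer depends on w. The truncation at the end of 2021 is offset by long waits carried in from before 2013.

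| Diagnoses captured before 2013 | True 12 | True 18 | True 24 |
|---|---|---|---|
| None | 10.0 | 13.5 | 16.1 |
| 5 years, steady | 11.9 | 17.4 | 22.2 |
| 10 years, steady | 12.0 | 17.9 | 23.7 |

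With 20 years of history and diagnoses growing by about 5% a year, a true 12 gives 11.2; at about 10% a year it gives 10.5.

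**Step 4, by year of diagnosis.** Within one diagnosis year nothing is carried in from earlier years. With a true median of 18, the Cohort 1 median falls from 17.5 months (2013) to about 3.1 months (2021) with no real change.

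**Step 5, combining the cohorts.** Restricted to diagnoses in 2013-2021, Kaplan-Meier on both cohorts together recovers true medians of 12, 18 and 24 as 12.0, 18.0 and 24.0. Without that restriction (ten years of earlier diagnoses, which enter only if 1L started in the window), it gives 13.8, 21.8 and 30.2. Combining alone is therefore not enough.

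**The case against.** The strongest reply concerns Cohort 1. A reader might infer from Step 2 that its median must be 17% to 33% too short. The documents do not support that. Nothing limits Cohort 1 to diagnoses from 2013, and Step 3 shows the shortfall nearly vanishing under steady diagnosis with ten years of history. Its size depends on growth in diagnoses and depth of capture, which the documents do not state. Short waits also shrink it: even with no earlier diagnoses, true medians of 2, 3 and 6 months give 1.95, 2.88 and 5.51. The visible text does not say whether the clock starts at initial or advanced diagnosis. The section that Protocol 9.7.3 cites for definitions (9.3.1.3) is not visible and may settle this, although it would not change the membership rules.

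It is also fair that a median among patients who started 1L is a legitimate description if labelled as such, that the fall across diagnosis years appears only in an optional subgroup (Protocol 9.7.4), and that this is one exploratory row in a descriptive study.

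All of that stands, and it limits the Cohort 1 part. It does not help Cohort 2, where the guaranteed event-free time is present whatever the diagnosis pattern. Nor does it supply the missing label or an estimate for DDLPS patients as a whole.

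**Conclusion.** The point holds in two parts of unequal strength.

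- **Cohort 2:** the median is wrong as an estimate of time to 1L. The direction follows from the membership rule alone. The size is illustrative: about 34 months for a true 12 under the Step 1 assumptions without death or loss, and longer or not reached in the other scenarios at that median.
- **Cohort 1:** the median is conditional on having received 1L by the cut-off. Whether it differs from the median in all eventual 1L users cannot be told from the documents (about 10 to about 12 for a true 12 in the cases above). It would be distorted if tabulated by year of diagnosis.

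Two wider readings should not be drawn. The Cohort 1 figure is not meaningless, only unlabelled. And OS from 1L in Cohort 1 is not touched, because its clock starts at 1L. The change is worth making because the row would mislead if produced as planned and the correction is cheap.

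**What to change.** In Table 7, replace the diagnosis-to-1L row with one cumulative incidence of 1L start in Cohorts 1 and 2 combined:

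- Restrict it to patients whose unresectable locally advanced or metastatic diagnosis is dated from 1 January 2013 to 31 December 2021, and count from that date. If the clock is to start at initial diagnosis, restrict to initial diagnoses in the same window. State which is used.
- If the advanced diagnosis is used, check whether Cohort 2 admits patients first diagnosed before 2013. If it does not, apply the same limit to the Cohort 1 patients in this row.
- Treat death before 1L as a competing event and censor at last activity.
- Report estimates at fixed times if the median is not reached. In the illustration this happens when 50% or 70% of patients never need 1L.

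Drop the Cohort 2 median. Keep the Cohort 1 median only if labelled as applying to patients who received 1L by the end of the identification period, and do not tabulate it by year of diagnosis.

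The cost is SAP wording and one more programmed estimate on data already planned. Patients diagnosed before 2013 leave this row.

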9.7.4. Subgroup analysis

The above analyses may be performed in additional subgroups for Cohort 1 and Cohort 2, pending sample size and feasibility. These include:

- Unresectable locally advanced DDLPS patients
- Metastatic DDLPS patients
- Brightline-1-like cohort including patients who received doxorubicin monotherapy or doxorubicin-based regimens as 1L treatment
- Real-world Brightline-1 cohort including patients matching the inclusion and exclusion criteria in Brightline-1 trial
- Additional subgroups, which may include age, sex, and year of initial diagnosis.

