Data analysis:	This study will be descriptive in nature. Continuous variables will be summarized using mean, standard deviation (SD), median and range. Categorical measures will be summarized using frequencies and percentages. OS will be estimated by the Kaplan-Meier (KM) method to obtain median estimates with two-sided 95% confidence intervals (CIs). OS may be assessed by line of therapy (LOT) and type of treatment received in each LOT, pending feasibility. Subgroup analyses will be conducted in both Cohort 1 and 2: • Unresectable locally advanced DDLPS patients • Metastatic DDLPS patients • Brightline-1-like cohort including patients who received doxorubicin monotherapy or doxorubicin-based regimens as 1L treatment. • Real-world Brightline-1 cohort including patients matching the inclusion and exclusion criteria in Brightline-1 trial • Additional subgroups pending feasibility, which may include age, sex, and year of diagnosis. Sensitivity analyses will be conducted: • to only include patients in areas covered by the National Mortality
	Database and with higher completeness on survival data • to only include patients before COVID-19 emergence (cohort identification period: January 1, 2013 – December 31, 2019) to assess the possible impact of COVID-19 pandemic on treatment patterns and outcomes
Milestones:	 Protocol approval: May 2023 Start of analysis: Dec 2023 End of analysis: Feb 2024 Final report of study results: Apr 2024

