9.2.3. Study visits

Definitions of relevant time periods are detailed below.

Study period: January 1, 2013 – December 31, 2022

Baseline period: All available data prior to index date

[figure not shown]
Cohort identification period: January 1, 2013 – December 31, 2021 (one year before end of study period)

Index date: The index date for Cohort 1 will set to the date of initiation of 1L treatment; the index date for Cohort 2 will be the date of initial DDLPS diagnosis during cohort identification period.

Follow-up period: From index date until date of death, if available, or the date of censoring if there is no record of death, whichever occurs first. For survival and treatment patterns, the date of censoring will be the last activity date, defined as the date of the last visit of any type prior to the end of the study period.

Figure 1 illustrates the time periods for the study timelines.

(a). Cohort 1

NIS Protocol BI Study Number 1403-0024

Page 14 of 37 C42272174

Proprietary confidential information© 2023 Boehringer Ingelheim GmbH or one or more of its affiliated companies (b). Cohort 2

[figure not shown]

Figure 1. Overall study period

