6.2 SETTING

In this study, patient data from NATDSS network from January 1, 2013 to December 31, 2022 will be used. Details of data source are described in section 8.

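### The Brightline-1-like subgroup is also listed for Cohort 2, where survival counted from diagnosis includes guaranteed survival up to a 2022 first-line start and is biased upwards

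*Protocol*

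**What the plan says.** Protocol 9.2.2 defines the second cohort: "Cohort 2 will include patients with DDLPS who have not initiated 1L systemic antineoplastic treatment by the end of cohort identification period". It keeps later starters there: "Patients initiated 1L treatment afterwards or patients received adjuvant and/or neoadjuvant therapy only through follow-up will be included in Cohort 2". The same section fixes what counts as first line: "1L therapy will be defined as the initial set of drugs used after unresectable locally advanced or metastatic diagnosis".

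Protocol 9.2.3 ends cohort identification on 31 December 2021 ("one year before end of study period"), and SAP 6.2 states that "patient data from NATDSS network from January 1, 2013 to December 31, 2022 will be used". On the time origin, Protocol 9.2.3 says that "the index date for Cohort 2 will be the date of initial DDLPS diagnosis during cohort identification period". Protocol 9.3.1.2 and 9.7.2, and SAP 10.1.2, estimate survival after initial diagnosis in both cohorts by Kaplan-Meier. The readable text mentions no delayed entry or landmark.

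Protocol 9.7.4 offers subgroup analyses for Cohorts 1 and 2 as an option, subject to sample size and feasibility. One subgroup is patients who "received doxorubicin monotherapy or doxorubicin-based regimens as 1L treatment". The abstract is firm: "Subgroup analyses will be conducted in both Cohort 1 and 2".

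**The concern.** Membership of this subgroup in Cohort 2 is decided by an event in 2022, but the survival clock starts at a diagnosis between 2013 and 2021. A patient who died before starting 1L cannot be a member, so no death can occur between diagnosis and 1L. Ordinary Kaplan-Meier nevertheless counts those months as time at risk.

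The result would not stand alone. SAP Annex 2 intends its tables and figures to be repeated for subgroups where feasible, and Table 4 and Figure 2 show survival from diagnosis for the two cohorts together. The Cohort 2 subgroup would look better than its Cohort 1 counterpart because of the cohort rule alone. Protocol 12 says that the results may supplement regulatory submissions, and the limitations in Protocol 9.9 do not mention this bias.

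**Working it through.** **The plan's own figures.** The plan gives no figure for this subgroup. Its only design figures are the precision table in Protocol 9.5. A simulated Kaplan-Meier median with a log-log interval and 20% censoring reproduces the rows tried to within about 1.3%: for N = 1500 and a median of 8 months, (7.40, 8.60) against the stated (7.419, 8.625). The point does not rest on that table, except that its medians of 8, 10 and 12 months from 1L serve as input below.

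**Step 1: who can qualify.** No 1L by 31 December 2021, 1L doxorubicin on record, and data ending 31 December 2022 together place the 1L start between 1 January and 31 December 2022. Follow-up after 1L is therefore at most 364 days.

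**Step 2: immortal share for one patient, from the dates.** Minimum share = (1L − diagnosis) / (31 Dec 2022 − diagnosis), for a patient followed to the end of the study.

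| Diagnosis | 1L start | Days to 1L / total days | Minimum share |
|---|---|---|---|
| 1 Jan 2013 | 1 Jan 2022 | 3287 / 3651 | 90% |
| 1 Jul 2020 | 1 Jul 2022 | 730 / 913 | 80% |
| 1 Jul 2021 | 1 Jan 2022 | 184 / 548 | 34% |
| 31 Dec 2021 | 1 Jan 2022 | 1 / 365 | 0.3% |

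The dates alone allow anything from almost none to almost all.

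**Step 3: the subgroup as a whole.** This needs assumptions that are not in the documents. Diagnosis X is uniform over months 0 to 108. Time to 1L, T, is exponential with a median of 3 to 24 months. Time to death without 1L, D, is exponential with a median of 24 to 60 months. Survival after 1L, P, is exponential with a median of 10 months (within the range in Protocol 9.5). Cohort 2 members have T < D and 108 < X + T < 120; Cohort 1 members have T < D and X + T ≤ 108. Follow-up is min(T + P, 120 − X), and the immortal share is the sum of T divided by the sum of follow-up. With median survival before 1L at 36 months:

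| Median time to 1L | Immortal share, Cohort 2 subgroup | 12-month KM from diagnosis, Cohort 2 subgroup | Same, Cohort 1 |
|---|---|---|---|
| 3 months | 54% | 72% | 58% |
| 6 months | 68% | 83% | 67% |
| 12 months | 78% | 90% | 76% |
| 24 months | 84% | 93% | 82% |

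Over the full grid, the immortal share is about 53 to 85%. Twelve-month survival is about 71 to 94% against 57 to 84%, and 24-month survival about 36 to 81% against 25 to 58%. P has the same distribution in both cohorts, so the gap comes from the selection rule.

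**Step 4: check of the remedy.** With the clock restarted at 1L in simulated Cohort 2 patients, Kaplan-Meier returns the assumed median: about 8.0 for 8 months and 9.9 to 10.0 for 10 months. For 12 months the median is not reached, because follow-up after 1L cannot exceed 12 months.

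**The case against.** A reader might infer that survival in this subgroup is almost all immortal time. The documents do not support that. Diagnosis can be as late as 31 December 2021, and if 1L usually follows soon after diagnosis, patients diagnosed in 2021 are the likeliest to qualify. A median gap of 2 months (median survival before 1L of 24 months) brings the share down to about 43%. A share of 93% needs diagnosis spread evenly over 2013 to 2021 and 1L spread evenly over 2022, regardless of when the patient was diagnosed.

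Other stronger readings also fail:
- Qualifying patients need not be untreated. Surgery and adjuvant or neoadjuvant therapy are allowed before 1L.
- Only one listed subgroup is defined by 1L doxorubicin. The eligibility criteria behind the real-world Brightline-1 cohort are not given, so whether it shares the problem cannot be judged.
- Nothing in the documents describes the arms of Brightline-1, so no statement about a trial comparator can be built on this.

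The best defence is that the analysis may never be run. Protocol 9.7.4 makes it optional, and in simulation only about 3 to 10% of 1L starters fall in the 2022 window, before restricting to doxorubicin. But the abstract is not conditional, and no minimum size is stated. SAP section 10.2 is absent from the public text, so a restriction there cannot be ruled out.

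It is also fair to say that Cohort 1 survival from diagnosis contains guaranteed survival up to 1L. Confining the subgroup to Cohort 1 without moving the clock would therefore not be enough.

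**Conclusion.** The point holds. As the readable plan stands, Cohort 2 survival in the Brightline-1-like subgroup is biased upwards, because membership requires survival from diagnosis to a 1L start in 2022. The direction follows from the stated dates and time origin. The size rests on assumed gaps to 1L and assumed survival before 1L. Under those in step 3, a substantial and often major share of follow-up is immortal, and 12-month survival is overstated by roughly 11 to 16 percentage points relative to Cohort 1 from diagnosis (for example 72 − 58 = 14 and 83 − 67 = 16). The primary outcome, overall survival from 1L in Cohort 1, is not affected, so this is a minor correction to a secondary display.

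**What to change.** In Protocol 9.7.4 and the abstract, and in SAP 10.2 if subgroups are handled there:

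1. Limit survival analyses of any subgroup defined by receipt of 1L to Cohort 1, with time zero at 1L start.
2. If survival from diagnosis is shown for such a subgroup in either cohort, use delayed entry (left truncation) at 1L start and report the numbers at risk, which may be small soon after diagnosis.
3. Keep the descriptive tables for Cohort 2 (treatment patterns, resource use, cost), and keep the disease-extent, age, sex and year-of-diagnosis subgroups.
4. Reconcile the optional wording in 9.7.4 with the firm wording in the abstract.

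The cost is a phrase in each place and the loss of one small Cohort 2 survival table, whose patients have at most 12 months of follow-up after 1L.

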9.3.1.2. Secondary outcomes

Survival after initial diagnosis

Outcome type: Secondary

• Outcome name: Survival after initial diagnosis

• **Time frame**: Time from initial diagnosis until the earliest record of death or end of the study period

• **Population**: Cohort 1, Cohort 2

NIS Protocol BI Study Number 1403-0024

Page 15 of 37 C42272174

Proprietary confidential information© 2023 Boehringer Ingelheim GmbH or one or more of its affiliated companies

Survival after initial diagnosis for each patient will be defined as the date of death minus the date of initial diagnosis. For patients with no record of death, survival after initial diagnosis will be censored at the last activity date before the end of the study period.

Description of treatment patterns

Outcome type: Secondary

• Outcome name: Treatment patterns

• Time frame: Treatment patterns are assessed at the index date and during follow-up

■ **Population**: Cohort 1, Cohort 2

The following variables of interest will be assessed to describe treatment patterns defined by LOT and regimens.

Treatment patterns by LOT and regimens

Variable	Definition	Timing
1L Treatment Type	Regimen name from LOT data for treatments with line number = 1, 2 and 3. Treatment types will be classified as follows, specific	
2L Treatment Type	treatments and categories may change upon examination of the data:	
	NCCN/CSCO preferred	
	 Doxorubicin 	
	Epirubicin	
	Liposomal doxorubicin	
	AD (doxorubicin, dacarbazine)	
	 AIM (doxorubicin, ifosfamide, mesna) 	Any time after index date
	Ifosfamide, epirubicin, mesna	
3L Treatment Type	 Larotrectinib (NTRK fusion pos sarcomas only) 	
	 Entrectinib (NTRK fusion pos sarcomas only) 	
	 Pazopanib 	
	Eribulin	
	Trabectedin	
	Other	
	AD LMS only (doxorubicin, dacarbazine)	
	Gemcitabine and docetaxel	

NIS Protocol BI Study Number 1403-0024 Page 16 of 37 C42272174

Proprietary confidential information© 2023 Boehringer Ingelheim GmbH or one or more of its affiliated companies

Variable	Definition	Timing
	Gemcitabine	
	Gemcitabine and vinorelbine	
	Gemcitabine and dacarbazine	
	Dacarbazine	
	• Ifosfamide	
	Temozolomide	
	 Vinorelbine 	
	Regorafenib	
	 MAID (mesna, doxorubicin, ifosfamide, dacarbazine) 	
	 Pembrolizumab 	
	 durvalumab 	
	• Other	
Total number of treatment lines	From LOT data, for all lines after index date, categorical variable defined as total of treatment lines reported.	Any time after index date

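### Year-of-diagnosis subgroups within each cohort would show a false fall in Cohort 1 survival after initial diagnosis, because the 31 December 2021 first-line deadline caps the diagnosis-to-treatment gap in recent years

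*Protocol*

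**What the plan says.** Cohort 1 takes patients with unresectable locally advanced or metastatic disease who "received at least one line of systemic antineoplastic treatment by the end of cohort identification period" (Protocol 9.2.2). Cohort 2 takes those "who have not initiated 1L systemic antineoplastic treatment by the end of cohort identification period". Late starters are assigned explicitly: "Patients initiated 1L treatment afterwards or patients received adjuvant and/or neoadjuvant therapy only through follow-up will be included in Cohort 2". The identification period ends on 31 December 2021 for everyone, whatever the diagnosis date, and follow-up runs to 31 December 2022 (Protocol 9.2.3). SAP 6.3 and 6.4 repeat these rules.

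Primary OS runs from the start of 1L in Cohort 1. The secondary outcome, survival after initial diagnosis, is planned for both cohorts with the time frame "Time from initial diagnosis until the earliest record of death or end of the study period" (Protocol 9.3.1.2).

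Protocol 9.7.4 states: "The above analyses may be performed in additional subgroups for Cohort 1 and Cohort 2, pending sample size and feasibility". Its last item is "Additional subgroups, which may include age, sex, and year of initial diagnosis". SAP Annex 2 says the mock tables will be replicated for subgroups where feasible.

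**The concern.** The cohorts are separated by calendar date, not by time since diagnosis, so the diagnosis year sets the longest gap that a Cohort 1 patient can have. Later years keep only fast starters in Cohort 1 and move slower starters to Cohort 2. Survival after diagnosis in Cohort 1 is the gap plus survival from 1L. Capping the first term shortens the sum.

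The study is meant to support a future New Drug Application (Protocol 7), and Protocol 9.7.5 sets out to assess the impact of COVID-19 on outcomes. A fall confined to patients diagnosed around 2020–2021 could easily be read as a pandemic effect or a real worsening. Protocol 9.9 does not mention this selection, and the visible text has neither a fixed diagnosis-to-1L window nor a method for delayed entry.

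**Working it through.** **1. Inputs from the documents.** Deadline 31 December 2021 and end of data 31 December 2022 (Protocol 9.2.3). Exponential OS from 1L with median 8, 10 or 12 months (Protocol 9.5). The only computed figures in the documents are the confidence limits in 9.5. All 24 reproduce within 0.64% using log-log limits and 20% censoring (N=1500, median 8: 7.402–8.620 against the stated 7.419–8.625). They supply the OS medians but do not address this point.

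**2. Assumptions.** The diagnosis-to-1L gap is an output of the study (Protocol 9.7.3), so it is taken as exponential with median g = 2, 6, 12 or 24 months. Diagnoses are uniform over 2013–2021 and true survival is the same in every year. 60% eventually start 1L, and those patients do not die before it. The rest have a 60-month median. Censoring is at the end of data only.

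**3. Who reaches Cohort 1.** For a diagnosis year whose time to the deadline is uniform between a and a+12 months, with λ = ln 2 / g:

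share = 1 − (2^(−a/g) − 2^(−(a+12)/g)) / (12λ)

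Here a = 0 for 2021, 12 for 2020 and 96 for 2013. For 2021 and g = 12: 1 − (1 − 0.5)/0.693 = 0.28.

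| Median gap g | 2013 | 2020 | 2021 |
|---|---|---|---|
| 2 | 1.00 | 1.00 | 0.76 |
| 6 | 1.00 | 0.86 | 0.46 |
| 12 | 1.00 | 0.64 | 0.28 |
| 24 | 0.95 | 0.40 | 0.15 |

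**4. Cohort 1 survival after initial diagnosis.** Simulated Kaplan-Meier medians in months, OS from 1L 10 months, no true trend:

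| Median gap g | 2013 | 2021 |
|---|---|---|
| 2 | 13.2 | 12.1 |
| 6 | 19.1 | 13.3 |
| 12 | 26.3 | 14.1 |
| 24 | 37.3 | 13.9 |

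Repeat runs differ by up to about 0.4 months. At g = 12 one run gives 26.6 (2013), 25.5 (2017), 22.3 (2019), 18.5 (2020) and 13.7 (2021). With an OS median of 8 or 12 months the fall is 24.1 to 11.8 or 28.9 to 16.3. At g = 2 essentially only 2021 moves.

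**5. Confirming the cause.** If the cohorts are instead defined by 1L within 12 months of diagnosis, for diagnoses to the end of 2020, the trend disappears. At g = 12 the medians are 15.8 (2013), 15.7 (2017), 15.8 (2019) and 15.8 (2020).

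**6. OS from 1L.** If the gap is unrelated to later survival, medians by diagnosis year stay within 9.8–10.1 months (g = 12). If fast starters do worse (shared log-normal frailty, SD 0.7), the median falls from 9.2 to 6.7.

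**7. Cohort 2.** Among 2021 diagnoses, future 1L starters make up 26%, 44%, 52% and 56% for g = 2, 6, 12 and 24, against 0 to 7% in 2013. From 2013 to 2021, 12-month survival moves from 0.87 to 0.81 (g = 2), 0.86 (g = 6) or 0.90 (g = 12). It rises from 0.43 to 0.69 at g = 12 if never-treated patients have a 10-month median. The direction is therefore not fixed.

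**8. Testing the remedy.** In the combined cohorts, 12-month survival is 0.84 in every diagnosis year (g = 12). OS by index year was tested in a model with g = 18 and an OS median of 8 months if 1L starts within 6 months of diagnosis, otherwise 12. It is flat (10.9–11.1) when patients diagnosed before 2013 are included. With none captured, it rises from 8.6 (2013) to 11.0 (2021).

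**The case against.** A reader might infer that primary OS by diagnosis year must be distorted, or that a false trend spans the whole decade. The documents support neither. They link the gap to prognosis nowhere, and without that link OS from 1L is flat. Even with the step-8 link, Cohort 1 median OS by diagnosis year is 10.96 months for 2013 and still 10.83 for 2018. Only the last two or three years move materially. Equally, the shift in Cohort 2 patient mix does not by itself establish a survival trend there.

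The cells are also small. In the step-8 model, 2021 diagnoses are 2.9% of Cohort 1, or about 44 patients at N=1500. An approximate 95% interval for their median OS, ignoring censoring, is 5.7–13.3 months. This stands as a reason for caution, but imprecision does not remove the bias, and pooling recent years narrows the interval around a value that is still biased.

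Finally, the subgroup is optional, the study is descriptive with no planned comparison of groups (Protocol 9.3), and SAP 10.2 is not visible, so a safeguard there cannot be excluded. These points limit the weight of the concern. They do not make the within-cohort trend interpretable if it is reported.

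**Conclusion.** The concern holds in a limited form. That diagnosis year caps the gap follows directly from the cohort rules. A false fall in Cohort 1 survival after initial diagnosis appeared in every scenario run: about 1 month between 2013 and 2021 if the median gap is 2 months, about 6 months if it is 6, and about 12 months if it is 12. The size rests on the assumed gap. With a short gap the effect is confined to the latest diagnosis years. With a gap of 12 to 24 months it reaches back to about 2017 or earlier.

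The effect on OS from 1L is conditional on a link between gap and prognosis. In Cohort 2 the change in mix is certain, but the size and direction of any survival trend are not. The main Cohort 1 OS estimate is not affected. This is worth correcting before analysis, as a point about an optional subgroup.

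**What to change.** In Protocol 9.7.4 and the SAP:

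- Report survival after initial diagnosis by diagnosis year only in Cohorts 1 and 2 combined, restricted to diagnoses in 2013–2021, and not within each cohort. The restriction is needed because Cohort 1 may contain earlier diagnoses, while Cohort 2 is indexed at a diagnosis within the identification period.
- For Cohort 1 OS, replace year of initial diagnosis with index year, which SAP Table 1 already lists. First check that patients diagnosed before 2013 are captured, using the pre-2013 row in SAP Table 2 broken down by index year. If they are not captured, do not interpret the earliest index years, which could show the mirror-image bias. Index year answers a slightly different question (when treatment began), and the report should say so.

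The cost is a few lines of text and one extra tabulation. No new data are needed, and neither the cohort definitions nor the main analysis changes.
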